4.5.2.3 Time to Clinical Response

Time to clinical response will be based upon hospital discharge, fever, and oxygen saturation, and two or more of the following: improved respiratory status, heart rate, or systolic blood pressure ([Marty et al. 2017](#)). Time to clinical response is defined as the time from start of study treatment until the timepoint where "clinical response", as defined below, is met.

Patient should meet conditions A and B, and (2 of C, D and E) OR F below. For patients who achieve four of the five vital sign resolution criteria above each of these must be maintained for 24 hours for the clinical response endpoint to be met. As for the primary endpoint, missing data will not be imputed.

A. Temperature

$\leq 38.6^{\circ}\text{C}$ ($\leq 102^{\circ}\text{F}$) if axillary, or

$\leq 37.2^{\circ}\text{C}$ ($\leq 99^{\circ}\text{F}$) if oral, or

$\leq 37.7^{\circ}\text{C}$ ($\leq 100^{\circ}\text{F}$) if rectal, core, temporal or tympanic

- without use of antipyretics within 8 hours (missing antipyretics will be assumed to have been taken)

B. Oxygen Saturation

$\geq 95\%$ (without supplemental oxygen)*+

*This requirement will be waived for patients with a history of chronic supplemental oxygen requirement who had a baseline oxygen saturation $< 95\%$ with supplemental oxygen, within 12 months of enrolment as documented in the patient's medical records.

+A patient with a history of chronic hypoxia (without supplemental oxygen) can satisfy the normalisation criteria for oxygen saturation if the value (without supplemental oxygen) was $\leq 2\%$ from patient's historical oxygen saturation baseline as recorded within 12 months before enrolment and documented in the patient's medical records.

C Respiratory Status:

- I. Return to pre-morbid oxygen requirement (patients with chronic oxygen use), OR
- II. Need for supplemental oxygen (given in any way—ventilator, non-invasive ventilation, facemask, face-tent, or nasal cannula) to no need for supplemental oxygen, OR
- III. Respiratory rate ≤ 24 per min (without supplemental oxygen)

D Heart Rate

≤ 100 beats per min

E Systolic blood pressure

≥ 90 mmHg, without inotropic support given within 2 hours of assessment

OR

F Hospital Discharge

TTCR is calculated as per [Table 6](#).

Table 6 TTCR Calculation

TTCR based on	TTCR (hours)
A and B and (2 of C, D and E) met for 24 hours	date time of initial vital signs assessment where 4 out of 5 criteria initially met and subsequently maintained for 24 hours - start treatment date time
A and B and (2 of C, D and E) met prior to discharge*	date time of initial vital signs assessment where 4 out of 5 criteria initially met and subsequently discharged - start treatment date time
Hospital discharge	date time of hospital discharge - start date time of treatment

TTCR=Time to Clinical Response.

*when a patient met vital sign criteria and was discharged from hospital during the 24 hour period of stability confirmation, the time of achieving TTCR was defined as the initial time at which vital signs were resolved and not the time of hospital discharge.

The time to clinical response will be compared between the baloxavir marboxil plus SOC NAI and matching placebo plus SOC NAI arms using the stratified log-rank test within three regions (i.e. North America, EMEA, ROW), NEWS2 at baseline (≤ 7 , > 7), and time from symptom onset to study treatment (≤ 48 hours, > 48 hours) included as the stratification factors. The Kaplan Meier plot, median time to response, 95% CIs, and p-values will be presented.

The log-rank test is most appropriate when the assumption of proportional hazards is met. The proportional hazards assumption will be tested graphically using the log cumulative hazard plot by treatment group. The plots for each treatment group will be parallel if the proportional hazard assumption holds. Should the proportional hazards assumption be violated the Gehan Wilcoxon test will be used to analyze the data.

The estimand is the difference in distributions between baloxavir marboxil plus SOC NAI and matching placebo plus SOC NAI arms in the mITTi for the time to clinical response, using appropriate method, as described above. This absolute measure will be assessed over the duration of the study (35 days). The median TTCR for each treatment group and difference between treatment groups will be presented.

Intercurrent events are those that occur after treatment initiation and either preclude observation of the variable or affect its interpretation. Intercurrent events, such as patients who are lost to follow-up, die or discontinue for any reason prior to achieving a clinical improvement or do not have a clinical improvement event, will be accounted for through censoring rules, as described in [Table 7](#) below.

Table 7 TTCR and Censoring

Event	Censor	Date and Time
Clinical Response (based on vital signs assessments)	No	first vital signs assessment where 4 out of 5 criteria initially met and subsequently maintained for 24 hours period
Clinical Response (based on vital signs criteria met prior to discharge)	No	first vital signs assessment where 4 out of 5 criteria initially met and maintained prior to discharge
Clinical Response (based on hospital discharge)		
- hospital discharge to another hospital (i.e. hospital admission within 24 hours) and discontinue study on same day	Yes	hospital discharge
- hospital discharge to another hospital (i.e. hospital admission within 24 hours) and continue study	Yes	hospital discharge
- hospital discharge against medical advice	Yes	hospital discharge
- all other hospital discharge	No	hospital discharge
Death prior to achieving a clinical response	Yes	last vital signs assessment prior to death
Discontinuation for any reason prior to achieving a clinical response	Yes	last vital signs assessment prior to discontinuation
Lost to follow-up	Yes	last vital signs assessment
No clinical response	Yes	last vital signs assessment

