4.5.4 Vital Signs

Vital signs will include measurements of respiratory rate, pulse rate, peripheral oxygen saturation, systolic and diastolic blood pressures, and body temperature. Body temperature should be measured using the same methodology throughout the study.

For patients requiring supplemental oxygen, the oxygen flow rate (L/min) and/or fraction of inspired oxygen (FiO_2) should be recorded.

All of the vital sign parameters should be recorded *together* four times per day for the duration of the hospitalization throughout the treatment period (Day 1/Visit 1 to Day 10). It is recommended that the collection timepoints for vital signs and assessments (specific to NEWS2, Section 4.5.4) are spread throughout the study day to reflect the patient's condition over the entire study day, where possible. Following hospital discharge during the treatment period (Day 1 to Day 10) these parameters should be recorded once at each return visit to the clinic. Patients who remain hospitalized during the follow-up period (Day 11+) require daily collection of vital signs for the purpose of the study. During the follow-up period in patients who have been discharged, vital sign measurements and temperature are to be recorded at the investigators' discretion (e.g., if symptoms and signs persist during follow-up). Vital sign measurements may be performed by an MN professional.

4.5.5 Assessments Specific to National Early Warning Score 2

In addition to the vital measurements, the patient's consciousness level and the presence or absence of respiratory support must be recorded. The NEWS2 parameter for respiratory support is the selection of either air or oxygen –“oxygen” can include other forms of ventilation to maintain oxygen saturation (see [Appendix 3](#)).

These should be recorded at the same time points as the vital sign measurements (see Section 4.5.4 and [Appendix 1](#)).

4.5.6 National Early Warning Score 2

The NEWS2 should be calculated by the site at screening only based upon vital sign values and assessments related to National Early Warning Score 2 (see Section 4.5.5) recorded during the patient assessment. Should these assessments be conducted more than once during the screening period (per site patient care), all data collected closest to but before randomization should be used for the NEWS2 score calculation and assessment of patient eligibility. See [Appendix 3](#) for calculation instructions.

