6.4.2 Key Secondary Endpoints

6.4.2.1 *6-Point Ordinal Scale Measured at Day 7*

For the key secondary endpoint of 6-point ordinal scale the response rate of the scale will be measured at Day 7. The 6-point ordinal scale will be analyzed using the Cochran-Mantel-Haenszel test statistic stratified by region (i.e., North America, EMEA, ROW), NEWS2 (≤ 7 , > 7), and time from symptom onset to study treatment (≤ 48 hours, > 48 hours).

For the ordinal endpoint, missing data will be imputed by using the patient's last non-missing score for any patient with a missing response at Day 7. If the patient died

prior to Day 7, the patient will be included in the death category. The proportion of patients with a response in each category will be summarized by treatment group and Cochran-Mantel-Haenszel test statistic result presented.

A sensitivity analysis will be conducted where missing scores at Day 7 will be replaced by the patient's last non-missing score +1 (*i.e.*, *one ordinal category worse*). If the patient died prior to or on Day 7, the patient will be included in the death category.

6.4.2.2 *Time to Clinical Response*

The additional key secondary endpoint of the "time to clinical response" will be based upon hospital discharge, fever, and oxygen saturation, and two or more of the following: improved respiratory status, heart rate, or systolic blood pressure. The exact criteria for each parameter are as follows:

Temperature:^a

- $\leq 36.6^{\circ}\text{C}$ ($\leq 97.9^{\circ}\text{F}$)—axillary, or
- $\leq 37.2^{\circ}\text{C}$ ($\leq 99^{\circ}\text{F}$)—oral, or
- $\leq 37.7^{\circ}\text{C}$ ($\leq 99.9^{\circ}\text{F}$)—rectal, core, or tympanic

AND

Oxygen Saturation:^{b,c}

- $\geq 95\%$ (without supplemental oxygen)

AND two of the following three:

Respiratory Status:

- Return to pre-morbid oxygen requirement (patients with chronic oxygen use), OR
- Need for supplemental oxygen (given in any way—ventilator, non-invasive ventilation, facemask, face-tent, or nasal cannula) to no need for supplemental oxygen, OR
- Respiratory rate ≤ 24 per min (without supplemental oxygen)

Heart Rate:

- ≤ 100 beats per min

Systolic blood pressure:^d

- ≥ 90 mmHg
- OR

Hospital Discharge

- a Without the use of antipyretics within 8 hours.

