
 To evaluate the polymorphic and treatment-emergent amino acid substitutions in the PA, PB1, PB2, and NA genes and drug susceptibility in patients with evaluable virus 	
 Polymorphic and treatment-emergent amino acid substitutions in the PA, PB1, PB2, and NA genes Drug susceptibility in patients with evaluable virus

Table 1 Objectives and Corresponding Endpoints (cont.)

Safety Objective	Corresponding Endpoints

 To evaluate the safety of baloxavir marboxil plus a SOC NAI compared with matching placebo plus a SOC NAI in hospitalized patients with influenza 	
 Compare the incidence and severity of AEs and SAEs Incidence of AEs leading to discontinuation Proportion of patients with any post-treatment ALT and AST above baseline and $>3 \times \text{ULN}$, $>5 \times \text{ULN}$, $>10 \times \text{ULN}$
Pharmacokinetic Objective	Corresponding Endpoints

 To evaluate the single- and multiple-dose pharmacokinetics of baloxavir 	
 Plasma concentrations of baloxavir (active metabolite) at specified timepoints After each dose, concentration at predose and 24 hours postdose will be summarized Non-compartmental PK parameters such as AUC, C_{max} and $t_{1/2}$ (only for patients undergoing sequential PK sampling)
Exploratory Palatability Objective	Corresponding Endpoint

 To evaluate palatability of the oral suspension in hospitalized patients with influenza 	
 Number and proportion of patients reporting each palatability and acceptability response at each timepoint

AE=adverse event; AUC=area under the concentration-time curve; C_{max} =maximum plasma concentration; ICU = intensive care unit; NAI=neuraminidase inhibitor; NEWS2=National Early Warning Score 2; PK=pharmacokinetic; RT-PCR=reverse transcriptase polymerase chain reaction; SAE=serious adverse event; SOC=standard-of-care; $t_{1/2}$ =half-life; TTCl=time to clinical improvement; ULN=upper limited normal.

^a Criteria for each parameter noted in Section 6.4.2 of the Clinical Study Protocol (CSP).

^b Incidence of post-treatment influenza-related complications as defined in Section 6.4.3 of the CSP.

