3.3 DEVIATIONS FROM PROTOCOL

Since the finalization of the Protocol v2.0, the following updates have been made to the planned analysis:

Planned Interim Analysis

The statistic used to determine futility in the planned interim analysis per Protocol v2.0 was the hazard ratio:

- If the hazard ratio seen at the interim is below the calculated futility bound, the trial may be declared futile and recruitment will be stopped.

This has been updated to the p-value, to ensure consistency between the proportional hazards and non-proportional hazards scenarios in the analysis:

- If the p-value seen at the interim is above the calculated futility bound, the trial may be declared futile and recruitment will be stopped.

Clinical Response Definition

Clinical Response is defined per protocol as:

- For patients who achieve four of the five vital sign resolution criteria, both the temperature and oxygen saturation response criteria must be maintained for 24 hours for the clinical response endpoint to be met or hospital discharge, whichever occurs first.

This has been updated to:

- Clinical response is defined as resolution of at least 4 of the 5 vital signs within the respective resolution criteria, maintained for at least 24 hours, or hospital discharge, whichever occurs first.

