Appendix 4 National Early Warning Score 2 (NEWS2)

Physiological parameter	Score						
	3	2	1	0	1	2	3
Respiration rate (per minute)	≤8		9–11	12–20		21–24	≥25
SpO ₂ Scale 1 (%)	≤91	92–93	94–95	≥96			
SpO ₂ Scale 2 (%)	≤83	84–85	86–87	88–92 ≥93 on air	93–94 on oxygen	95–96 on oxygen	≥97 on oxygen
Air or oxygen?		Oxygen		Air			
Systolic blood pressure (mmHg)	≤90	91–100	101–110	111–219			≥220
Pulse (per minute)	≤40		41–50	51–90	91–110	111–130	≥131
Consciousness				Alert			CVPU
Temperature (°C)	≤35.0		35.1–36.0	36.1–38.0	38.1–39.0	≥39.1	

Reference

Royal College of Physicians. National early warning score (NEWS) 2 Standardizing the assessment of acute-illness severity in the NHS. London: RCP, 2017.

At screening, the NEWS2 should be calculated based upon vital sign values recorded during the patient assessment. *Should these vital signs assessments be recorded more than once during the screening period (per site patient care) all data collected closest to but before randomization should be used for the NEWS2 score calculation and assessment of patient eligibility.*

The oxygen saturation should be scored according to either the SpO₂ Scale 1 or 2 presented in the table above. The SpO₂ Scale 2 is for patients with a target oxygen saturation requirement of 88%–92% (e.g., in patients with hypercapnic respiratory failure related to advanced lung diseases, such as chronic obstructive pulmonary disease [COPD]). This should only be used in patients confirmed to have hypercapnic respiratory failure by blood gas analysis on either a prior or their current hospital admission.

The decision to use the SpO₂ Scale 2 should be made by the treating physician and should be recorded in the eCRF. In all other circumstances, the SpO₂ Scale 1 should be used.

For physiological parameter “Air or Oxygen?”: Any patients requiring the use of oxygen or other forms of ventilation to maintain oxygen saturations and support respiration should be assigned a score of 2.

The consciousness level should be recorded according to the best clinical condition of the patient during the assessment. Patients who are assessed as “Alert” (A) should be assigned a score of 0. Patients assessed as “New Confusion” (C), “Responsive to Voice” (V), “Responsive to Pain” (P), or “Unconscious” should be assigned a score of 3.

Scores should be assigned for respiratory rate, systolic blood pressure, pulse, and temperature according to the table above.

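### The SAP's axillary temperature limit for Time to Clinical Response is 2.0°C above the protocol's, is not declared as a change, and exceeds the SAP's own oral and core limits

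*SAP*

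**What the plan says.** Protocol 6.4.2.2 gives route-specific temperature limits for Time to Clinical Response. The axillary limit is "\leq 36.6^{\circ}\text{C}$ ($\leq 97.9^{\circ}\text{F}$)—axillary", followed by 37.2°C for oral and 37.7°C for rectal, core or tympanic readings.

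SAP 4.5.2.3, criterion A, gives the axillary limit as "\leq 38.6^{\circ}\text{C}$ ($\leq 102^{\circ}\text{F}$) if axillary". It keeps the protocol's Celsius limits for the other routes, for example "\leq 37.2^{\circ}\text{C}$ ($\leq 99^{\circ}\text{F}$) if oral", and adds temporal readings to the 37.7°C group.

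In the SAP a vital-sign response needs A (temperature) and B (oxygen saturation) and two of C, D and E, and "each of these must be maintained for 24 hours for the clinical response endpoint to be met". Hospital discharge is the alternative way to respond.

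SAP 3.3 opens with "Since the finalization of the Protocol v2.0, the following updates have been made to the planned analysis" and lists two: the interim futility statistic, and the 24-hour maintenance rule for clinical response. No temperature limit appears there. Note a to SAP Table 1 still sends the reader to the protocol: "Criteria for each parameter noted in Section 6.4.2 of the Clinical Study Protocol (CSP".

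**The concern.** Two controlling documents give incompatible limits for a mandatory component of an endpoint in the alpha-controlled testing sequence. The SAP edited the definition of this same endpoint in its list of departures and did not mention the limit.

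The SAP value also makes no sense beside its neighbours. In the protocol the axillary limit is the lowest of the three routes. In the SAP it is the highest, so the route of measurement decides whether a clearly raised temperature counts as resolved.

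Under the SAP limit, an axillary reading from 36.7 to 38.6°C neither delays the first qualifying assessment nor breaks the 24-hour run. Where temperature is the last sign to settle, the response is dated earlier than under the protocol. Protocol 4.5.4 asks that "Body temperature should be measured using the same methodology throughout the study", so for a patient measured at the axilla the looser limit would apply to every reading. The antipyretic sensitivity analysis in SAP 4.5.2.3.1 would remove one of the remaining safeguards, and the adolescent summary in SAP 4.9.2 reports the same endpoint.

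If the discrepancy were found only after unblinding, the choice between the two limits could look like a choice between results.

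**Working it through.** **Inputs**, from Protocol 6.4.2.2 and SAP 4.5.2.3 A:

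| Route | Protocol | SAP | SAP minus protocol |
|---|---|---|---|
| Axillary | 36.6°C (97.9°F) | 38.6°C (102°F) | +2.0°C (+4.1°F) |
| Oral | 37.2°C (99°F) | 37.2°C (99°F) | 0 |
| Rectal, core, tympanic | 37.7°C (99.9°F) | 37.7°C (100°F), temporal added | 0°C (+0.1°F) |

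**Step 1: unit check.** F = C × 9/5 + 32.
- 36.6°C gives 97.88°F, which reproduces the protocol's 97.9°F.
- 37.2°C gives 98.96°F, which agrees with 99°F in both documents.
- 37.7°C gives 99.86°F; the protocol prints 99.9°F and the SAP 100°F.
- 38.6°C gives 101.48°F; the SAP prints 102°F, and (102 − 32) × 5/9 = 38.89°C.

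The protocol's pair agrees to the printed digit. The SAP's three Fahrenheit values fit rounding up to a whole degree, so its 102°F appears to have been converted from 38.6°C. As both units differ from the protocol, one digit misread from the PDF is an unlikely explanation. The SAP's Celsius and Fahrenheit axillary limits also differ from each other by 38.89 − 38.6 = 0.29°C.

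**Step 2: order of the routes.**
- Protocol: axillary 36.6 < oral 37.2 < core 37.7°C.
- SAP: oral 37.2 < core 37.7 < axillary 38.6°C.
- Within the SAP, axillary minus oral is 38.6 − 37.2 = 1.4°C, and axillary minus core is 38.6 − 37.7 = 0.9°C.

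Example: an axillary 38.5°C meets criterion A; an oral 37.3°C fails it.

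**Step 3: readings that change status.** At 0.1°C resolution, the axillary values failing under the protocol and passing under the SAP run from 36.7 to 38.6°C: (38.6 − 36.7)/0.1 + 1 = 20 values.

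**Step 4: how often the limit is applied.** Protocol 4.5.4 asks for four sets of vital signs a day in hospital to Day 10. A 24-hour run therefore spans four intervals, or about 4 to 5 readings, each judged against this limit. Temperature had to hold for 24 hours under the protocol rule as well, so the declared change in SAP 3.3 does not alter this step.

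**What cannot be computed.** The documents do not give the share of patients measured at the axilla or how often temperature is the limiting criterion. No shift in median time to response, and no effect on the arm contrast, can be derived.

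**The case against.** The strongest reply is that the cause is unknown and the reach is small.

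On cause: criterion A in the SAP was edited elsewhere too, with temporal readings added and 99.9°F becoming 100°F. The SAP also cites a published trial for this endpoint, whose criteria are not available here. The documents therefore prove a contradiction, not a slip of transcription. That stands, and the fix has to allow for an intended change.

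On reach: the endpoint is third in the sequence and confirmatory only if the primary endpoint and the Day 7 ordinal scale both succeed. Neither the primary endpoint nor the futility analysis uses this limit. It applies alike to both blinded arms, so neither a direction of bias nor an inflated type I error is shown. A patient is affected only if measured at the axilla, with temperature limiting, no antipyretic within 8 hours (missing use counts as taken), and all other requirements met for 24 hours. This limits the consequence but does not settle which limit is in force. The count of 20 values describes the rule and is not an effect size.

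Three further points carry no weight for the finding:
- The SAP amendment rationale covers changes between SAP versions, so its silence on the limit proves nothing; SAP 3.3 is the relevant list.
- Note a to Table 1 is a cross-reference. It shows that the SAP still relies on the protocol's criteria, but it is not a second printed limit.
- An axillary 38.1–38.6°C scores 1 point on NEWS2, but that is no evidence of error. The endpoint also accepts a heart rate of 91–100 (1 point), a respiratory rate of 21–24 (2 points) and a systolic pressure of 91–100 mmHg (2 points).

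**Conclusion.** The concern holds. The axillary limit in SAP 4.5.2.3 contradicts Protocol 6.4.2.2 by 2.0°C, is not among the departures in SAP 3.3, and reverses the order of the routes within the SAP itself. This rests on a direct reading of the two texts and needs no outside assumption. A transcription error is the likely cause but is not proven.

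It must be fixed before unblinding because a mandatory part of an alpha-controlled endpoint has two definitions, and the result could depend on which one is programmed. The size of any effect on the result is unknown.

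**What to change.** Before unblinding:

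1. In SAP 4.5.2.3, criterion A, restore the protocol's axillary limit of 36.6°C (97.9°F).
2. Check the constant in the analysis programs, including how Fahrenheit readings are handled, since 38.6°C and 102°F are not the same temperature.
3. In the same edit, align 100°F with the protocol's 99.9°F, and list the added temporal route in SAP 3.3 if it is kept.
4. If 38.6°C was intended, declare and justify it in SAP 3.3, explain why it exceeds the oral and core limits, and correct note a to Table 1.

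The essential cost is one line of SAP text and a check of one programmed constant; item 3 adds minor wording. No new data are needed, and sample size and the primary analysis do not change.
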